8.4.2 Secondary Outcomes

• Clinical outcomes:

1. Change in best-corrected near visual acuity (BCNVA), reading speed and contrast sensitivity from baseline.

• Health Economic Outcomes:

- Health related quality of life measured using EQ-5D-5L at randomisation, six and 12 months (17)
- 2. Vision-specific quality of life measured using Impact of Vision Profile (IVI) at randomisation, six and 12 months (18)
- 3. Health service use and associated costs measured at six months and 12 months
- 4. Participant out-of-pocket costs measured at six months and 12 months.
- **Safety of the device:** The safety of device will be assessed postoperatively by noting any surgical complications during or after surgery and at each subsequent visit, including any reduction in visual acuity, position of the device, and corneal clarity. The endothelial cell density will be assessed at baseline and at 12 months (13-16).

• Mechanistic evaluation:

- 1. Correlation of participant ocular parameters such as scar size and volume with outcomes
- 2. Correlation of Preferred Retinal Locus (PRL) and ocular dominance with outcomes
- 3. Evaluation of the role of binocularity and visual summation on outcomes.

8.5 Participant Timeline

Eligibility will be determined at the screening visits. Surgery in Group 1 will take place at Day 0 with surgical review on days one and seven and study visits for both Groups at months one, three, six and 12. As the presence of the device is obvious to the casual observer, it will not be possible to mask assessors. Participants can also not be masked to the intervention. However, the final BCDVA measurement at 12 months will be duplicated by an additional observer independent to the trial and this measurement will be used for the primary analysis. BCDVA (primary outcome) will be measured with 4-meter ETDRS charts. Assessment at screening will include medical history, ophthalmic examination, confrontation visual field testing, visual acuity, reading speed, refraction, contrast sensitivity, assessment with x2.5 external telescope for distance and near vision, assessment for ocular dominance, binocular visual function, endothelial cell density, ocular coherence tomography (OCT) with volume scan, colour fundus photography, IVI, and EQ-5D-5L. Fundus fluorescein angiography (FFA) will be carried out in addition to OCT at baseline and only subsequently if clinically indicated as OCT cannot be performed post implantation of the device. The order of screening examinations will follow as per Figures 3 and 4, however, this may vary at site depending on the location of equipment. The detailed schedule is shown below in Table 2.

If all inclusion criteria are met at both screening visits, participants will be enrolled into the study. The required clinical information will be returned to the lead site (NICTU) and the study eye will be selected. The participant will be informed within 72 hours regarding which eye has been selected as the study eye and will be provided with a date to attend for Nd:YAG capsulotomy in the study eye, if not already done. After the participant has undergone the laser treatment, the Principal Investigator (PI) or designee will contact the CTU to determine group allocation. The participant will then be notified within 72 hours post laser treatment regarding group allocation.

Group 1 Care Pathway:

- Day 0: Surgery (surgical implantation of OriLens device)
- Day 1: Surgical review
- Day 7: Surgical review
- Assessments will be carried out at Months 1, 3, 6 and 12
- Low vision training at months 1, 3 and 12

Group 2 Care Pathway

- Day 0: No procedure
- Assessments will be carried out at Months 1, 3, 6 and 12 (beginning approximately six weeks post randomisation)
- Low vision training at months 1, 3 and 12

Figure 2. Study Schematic Diagram

[figure not shown]

Table 2. Schedule of enrolment, interventions and assessments

TIMEPOINT	Screening									v	, v	*
	Pre- screen	Screening 1 Day -45 to -20	Screening 2 Day -45 to -20	Day -20 to -7	Dау -7 to -1	Day 0	Day 1	Day 7	Month 1*	Month 3*	Month 6*	Month 12*
Pre-screening Questionnaire	Х											
Informed consent		х										
Medical History [†]		х			XX		XX	ХХ	Х	Х	Х	Х
Ophthalmic Examination‡		х			XX		XX	ХХ	Х	Х	Х	Х
Visual field by confrontation		х										
Visual Acuity (Distance)		х			XX		XX	XX	Х	х	х	Х
Visual Acuity (near), reading speed		х						XX	Х	х	х	Х
Refraction, contrast sensitivity		х						ХХ	Х	Х	Х	Х
Testing with external telescope		х										
Fundus photography		х										Х
ОСТ		х										
FFA		х										
Specular microscopy			х									Х
Microperimetry			х									
Assessment of PRL			х									
Orthoptic assessment #			х									
EQ-5D-5L			х								х	Х
IVI			х								х	Х
Health service use questionnaire											х	Х
Eye Selection confirmation				х								
Nd:YAG Capsulotomy (if required)				Х								
Randomisation				Х								
Informed consent for surgery					ХХ							
Surgical procedure ∞						ХХ						
Spectacle prescription & voucher for glasses									Х		Х	**
Visual Rehabilitation Training									Х	Х		х
Adverse Events Check							XX	XX	Х	х	х	Х

X: Both groups; XX: Intervention group; **: Spectacles dispensed at participants own cost; *: Control group Month 1- Approximately 6 to 8 weeks post randomisation, month 3- 14 weeks post randomisation, month 6- 6 to 7 months post randomisation, month 12- 12 to 13 months post randomisation; †: Medical history will include general medical history, ophthalmic medical history, blood pressure measurement and concomitant medication; ‡: Ophthalmic examination will include slit lamp assessment, pupillary assessment, intraocular pressure measurement and fundoscopy; #: Orthoptic assessment will include history of binocular vision anomalies, cover test, record of ocular movements, prism cover test, Bagolini glasses assessment, near point of convergence (NPC) assessment, measurement of horizontal fusional reserves and assessment of ocular dominance; ∞ : standard surgical report will be completed immediately post-op.

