8.3.1 Intervention description

Group 1: Intervention

The implantation of the OriLens device will be carried out as a secondary surgical procedure no more than eight weeks post randomisation. Participating surgeons will be trained in the surgical procedure for implantation at the beginning of the trial: an instructional video developed by the research team will be available and the CI may observe the first procedure at each site at the request of the PI. The degree of difficulty of this intervention is considered to be small for experienced cataract surgeons. The pupil will be dilated. Local anaesthetic will be used according to the individual surgeon's preference. A minimal incision of 5.5 millimetres is recommended. The wound can either be a scleral flap or tunnel according to the surgeon's preference. The anterior chamber will be filled with viscoelastic and the implant will also be covered in viscoelastic material before insertion. It is important that the optic does not come into contact with the forceps. The orientation of the device should be checked: the lens should vault backwards and the end of the superior haptic should point to the right. Both loops of the device are to be placed in the sulcus. Implantation should not proceed if there is evidence of zonular or existing intraocular lens instability. All viscoelastic will be removed at the end of the surgery. Closure of the incision will be according to surgeon's preference. A peripheral iridotomy is not a routine requirement but may be carried out at the surgeon's discretion. An intracameral injection of antibiotics and a subconjunctival injection of steroids will be administered according to the surgeon's preference. Post-operative management is similar to phacoemulsification surgery and is according to the surgeon's preference. Participants will be prescribed combined steroid/antibiotic drops for use four weeks post-operatively. A standard surgical report documenting the details above will be completed post-operatively.

If the pupil is <2.5 mm in diameter, small sphincterotomies should be performed at the time of implantation of the device. Recording of concomitant medications during medical history is required to determine presence of such which may have an effect on pupil size.

Refraction, spectacle prescription and provision and three 45 minute sessions of low vision training as per the trial manual will follow post-operatively as per section 10.2.

Group 2: Control

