Participants will receive refraction, spectacle prescription and low vision aid provision and three 45 minute sessions of low vision training as per the trial manual.

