10.2.2 Study Visits and Procedures

Pre-randomisation (Day -20 to -7) (Both groups)

Nd: YAG Capsulotomy in study eye (if not already done)

Pre-operative (Day -7 to -1) (Intervention group only)

Pre-op medical history assessment Visual acuity (distance only) and ophthalmic examination Informed consent for surgical procedure

Day 0 (Intervention group only)

Surgical procedure Standard surgical report (post-operatively)

Day 1 Post-operative (Intervention group only)

Medical history, ophthalmic examination Visual acuity (Distance only) Adverse events check

Day 7 Post-operative (Intervention group only)

Medical history, ophthalmic examination

Visual acuity (distance and near), reading speed, refraction, and contrast sensitivity Adverse events check

1 Month (approximately 6-8 weeks post randomisation) (Both groups)

Medical history, ophthalmic examination Visual Acuity (distance and near), reading speed, refraction, and contrast sensitivity Spectacle prescription dispensing and voucher for glasses Visual Rehabilitation training Adverse events check

3 months (approximately 14 weeks post randomisation) (Both groups)

Medical history, ophthalmic examination Visual Acuity (distance and near), reading speed, refraction, and contrast sensitivity Visual Rehabilitation training Adverse events check

6 months (approximately 6-7 months post randomisation) (Both groups)

Medical history, ophthalmic examination Visual Acuity (distance and near), reading speed, refraction, and contrast sensitivity Health related quality of life (EQ-5D-5L) Vision-related quality of life (IVI) Health service use questionnaire Spectacle prescription dispensing and voucher for glasses Adverse events check

12 months (approximately 12-13 months post randomisation) (Both groups)

Medical history, ophthalmic examination Visual Acuity (distance and near), reading speed, refraction, and contrast sensitivity Fundus photography Specular microscopy Health related quality of life (EQ-5D-5L) Vision-related quality of life (IVI) Health service use questionnaire Spectacle prescription dispensing Visual Rehabilitation training Adverse events check

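### The third of three low vision training sessions falls at the month-12 endpoint visit, so only two come before it; move it to the existing month-6 visit

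*Protocol*

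**What the plan says.** Protocol 8.3.1 defines the training content of both arms. For the implant group, "three 45 minute sessions of low vision training as per the trial manual will follow post-operatively". The control group receives "spectacle prescription and low vision aid provision and three 45 minute sessions of low vision training". Section 9.1 repeats three sessions as part of each allocated treatment. Section 8.3.2 gives the purpose of attendance as adapting to the device, and 10.4 says implant participants will be told that full adaptation requires the training.

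In 8.5 both care pathways carry the same line: "Low vision training at months 1, 3 and 12". Table 2 marks visual rehabilitation training for both groups at months 1, 3 and 12. The visit list in 10.2.2 matches. Its month-12 entry, after the vision tests and questionnaires, ends with "Health service use questionnaire Spectacle prescription dispensing Visual Rehabilitation training Adverse events check". Its month-6 entry, also for both groups, ends with "Health service use questionnaire Spectacle prescription dispensing and voucher for glasses Adverse events check" and contains no training.

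Month 12 is the primary time point (8.4.1, 10.6.2). It is also the last measurement of near acuity, reading speed, contrast sensitivity, IVI and EQ-5D-5L. No later efficacy visit is planned, and under 11.8 adverse event reporting stops at month 12.

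**The concern.** Training meant to help people adapt can show in an outcome only if it comes before that outcome, with time to take effect. A session at the final outcome visit cannot do this for anything the trial measures. If it follows the measurements, as the order of items in 10.2.2 suggests, it cannot influence them. If it comes first, it leaves no time for adaptation. No sentence fixes the order within the visit, but the conclusion is the same either way.

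What is at stake is what the month-12 results describe. Each arm is defined by three sessions, but the results would mainly reflect two, the second given about nine months before. Reading speed, near acuity and vision-specific quality of life are the outcomes where training could plausibly matter. The validity of the comparison between arms is not at stake, because the schedule is the same in both.

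**Working it through.** **Inputs from the protocol**
- Sessions per arm: 3 of 45 minutes each (8.3.1).
- Session times: months 1, 3 and 12 in both arms (8.5, Table 2, 10.2.2).
- Visit timing counted from randomisation. The Table 2 footnote reads "Control group Month 1- Approximately 6 to 8 weeks post randomisation, month 3- 14 weeks post randomisation", with month 6 at 6 to 7 months and month 12 at 12 to 13 months. Section 10.2.2 applies the same clock to both arms, for example "3 months (approximately 14 weeks post randomisation) (Both groups".
- Visit timing counted from surgery. Section 8.5 puts implantation at Day 0, and 8.3.1 allows surgery "no more than eight weeks post randomisation". The two clocks can therefore differ in the implant arm, and both are worked below.
- Conversion: one month = 365.25 / 12 / 7 = 4.348 weeks.

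**Training dose before the endpoint visit**
- Planned total: 3 × 45 = 135 minutes.
- Before month 12: 2 × 45 = 90 minutes; 90 / 135 = 67%.
- At month 12: 45 minutes; 45 / 135 = 33%.

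**Gap from the last earlier session (month 3) to the endpoint visit**
- From randomisation: 12 to 13 months = 52.2 to 56.5 weeks. Subtracting week 14 leaves 38.2 to 42.5 weeks, or 8.8 to 9.8 months.
- From surgery: (12 − 3) × 4.348 = 39.1 weeks.

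Both clocks give about nine months.

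**If the third session moves to month 6**
- Before month 12: 3 × 45 = 135 of 135 minutes.
- Gap from randomisation: month 6 to 7 = 26.1 to 30.4 weeks. The shortest gap to month 12 to 13 is 52.2 − 30.4, about 21.7 weeks on unrounded figures. The longest is 56.5 − 26.1 = 30.4 weeks. If both visits fall at the same point in their windows, it is 26.1 weeks.
- Gap from surgery: 6 × 4.348 = 26.1 weeks.

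**Sample size (8.6)**
- The plan's figure reproduces. With a difference of 8.06 letters, SD 13.4, two-sided 5% and 90% power, the required number is 59 per group. Allowing for 10% attrition, 59 / 0.9 = 65.6, rounded up to 66 per group and 132 in total.
- No training input enters this calculation, so moving the session leaves it unchanged.

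No effect on any outcome is estimated, because the protocol gives nothing to estimate it from.

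**The case against.** The strongest reply is that nothing is contradicted. Every place agrees on months 1, 3 and 12, and the protocol nowhere says that all three sessions must be finished before the endpoint. Section 8.3 explains the equal number of sessions as a guard against a placebo effect, and the schedule meets that aim. The trial tests the implant and not a number of sessions, and training is identical background in both arms. The primary outcome is letters read on a chart after refraction, with the expected gain attributed to the telescope, so it is probably the outcome least exposed to training. Moving the session gives it to controls as well, so any between-arm difference might not change. The trial manual, which is not part of the protocol, may give the order within the visit or a reason for a closing session.

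Most of this stands. The schedule is consistent and matched, there is no bias between arms, and no effect has been quantified. It does not answer the narrower point. The protocol gives the sessions a purpose and defines each arm by three of them, yet the third comes too late to serve that purpose for any measured result. The protocol states no reason for placing it there and plans no later assessment that could benefit from it.

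**Conclusion.** The concern holds. As written, two of three sessions (90 of 135 minutes, 67%) precede the endpoint visit, and the later of the two is 38 to 43 weeks before it, or 39 weeks if visits count from surgery. The month-12 results therefore mainly describe each arm after two sessions.

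This is a weakness in the design of the training schedule, not a threat to validity. The randomised comparison, type I error, sample size and intention-to-treat analysis are unaffected. An effect on reading speed, near acuity or the IVI is possible but of unknown size and direction. The conclusion rests on the visit windows in Table 2 and 10.2.2, and on the protocol text holding no unstated reason for a session at month 12. The change should be made because it costs little and brings the delivered training into line with the defined treatment.

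**What to change.** In 8.5 (both care pathways), Table 2 and 10.2.2, move the third session in both arms from month 12 to the existing month-6 visit, and state that it follows that visit's assessments. Month-6 data then still reflect two sessions, as now, and month-12 data reflect all three, with the last given about 26 weeks earlier (22 to 30 weeks from randomisation).

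The cost is an amendment to those three places and the rescheduling of one session at up to 10 sites. The month-6 visit becomes about 45 minutes longer and the month-12 visit shorter by the same amount. No extra session, visit or staff is needed, and the arms keep equal session numbers. The economic analysis does not change, because 10.6.3 leaves training costs out.

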8.6 Sample Size

As little information is available on improvement with secondary telescopic implants in pseudophakic eyes, the power calculations were based on improvements in BCDVA in participants with advanced AMD undergoing cataract surgery. Assuming from the previous IMT study that the telescope is capable of providing a 10 letter improvement for BCDVA from baseline and that standard care i.e., cataract surgery without the magnifying device will improve visual acuity by a mean (SD) of 1.94 (13.4) letters, 59 participants in each group would be required to detect a 8.06 letter difference between the two groups at 90% power, giving 66 per group accounting for 10 attrition (3, 8).

The power for the study is based on a minimum improvement of 10 letters expected from the telescope. This is in keeping with other studies such as the FDA-approved IMT study (3). However, as this is a comparative study with comparison to standard care i.e., cataract surgery with routine type IOL insertion, the difference expected will be eight letters. The choice of an eight letter difference is justified as follows:

An improvement of eight letters is clinically significant. Many studies in AMD use a 15 ETDRS letter change, which is doubling the visual angle, to assess the efficacy of interventions. It is proposed that half of this change is also clinically significant, according to the clinical experts in the team. It is certain that changes of less than five letters are not clinically significant, and this level of improvement is also considered not to be clinically significant by NICE. Data from previous studies confirm that the minimum number of letters required for repeatability of testing in normally-sighted individuals varies between 8-10 letters (19-21). In addition, Reeves et al (2009) have demonstrated that in vertepoforin photodynamic therapy, in participants with AMD, a five letter change in BCVA was associated with appreciable changes in vision-related and health-related QoL (HRQoL) (22). A difference of eight letters is also comparable to the range of improvement gained by participants with wet AMD during anti-VEGF treatment trials. Bressler et al (2010) report that in the landmark studies (MARINA and ANCHOR), an average improvement of 5-6 letters results in a detectable change in vision-related QoL (23). Although the mean improvement in BCVA following standard cataract surgery in participants with Advanced AMD has been shown to be 1.94 letters by Forooghian et al (2009) in the largest series, standard deviation is large at 13.4 letters (8). This large standard deviation is confirmed in fellow eyes which had intra-study cataract surgery in the IMT trial where the standard deviation was 13.5 letters (3). Given the large standard deviation in visual acuity outcomes following routine cataract surgery in this population, the least number of letters which gives test repeatability and that has been associated with an improvement in vision-related QoL has been selected as the primary endpoint in order to ensure that the trial is sufficiently powered.

8.7 Recruitment

8.7.1 Recruitment strategy

The study will be advertised on the NICTU website as well as on posters and flyers in Low Vision Clinics and Ophthalmology Clinics at each study site. The study email address, a contact telephone number, and details for the Research Nurse at each site will be provided for participants who would like more information. Upon request of information, potential participants will be sent a Research Ethics Committee (REC) approved Participant Information Leaflet (PIL), Information about NICE interventional procedure guidance (IPG) 272 and Pre-screening Questionnaire via email or post. In addition, the Macular Society will review the list of members who are on their research database to identify potential participants. The PI will also review the patient lists in the Low Vision Clinics. Potential participants will be contacted via mail to inform them of the study, invite them to

participate and provide them with the REC approved PIL, Information about NICE IPG 272 and prescreening questionnaire.

The recruitment period will last approximately 21 months with an initial lag time of three months. It is expected that 10 participants will be recruited in the first six months across all study sites with an increase in the number recruited per six-month block during the study period (see Study Timelines, table 1). It is anticipated that approximately 14 participants would be recruited at each study site, with the potential of generating a waiting list in the event of recruitment of higher than anticipated numbers. Recruitment progress will be monitored by the TMG.

8.7.2 Screening procedure

Potential participants will undergo a pre-screen to determine general suitability for the study. This will entail completion of a pre-screening questionnaire by an optometrist, ophthalmologist or General Practitioner (GP) of the potential participant's choosing. The completed pre-screening questionnaire will be sent by the potential participant to their nearest site and will subsequently be screened by the PI or delegated clinician as per the inclusion/exclusion criteria defined in the protocol. Potential participants will be sent a standard letter informing them that they may or may not be eligible for the study, dependant on further tests, and that the site will be in contact with them to arrange a suitable time to attend a screening appointment. Those who do not meet the initial inclusion criteria will be sent a standard letter to inform them of this.

Due to the number of screening examinations, two screening visits are required so as not to over burden the participant. The participant will not be expected to continue with screening if they do not meet the eligibility criteria as a result of any screening examination. It is anticipated that screening Visit 1 will last up to three hours and screening Visit 2, up to two hours. Those participants who meet the inclusion criteria and are enrolled into the study will receive reimbursement for their travel expenses at the end of the second screening visit. This will be a set amount for all participants.

Upon attending the first face-to-face screening appointment, the PI or designee will ask the potential participant whether they have any questions and whether they are still willing to participate in the study. If the patient agrees to participate, the PI or designee will obtain written informed consent prior to conducting screening tests. The following examinations will be conducted during the screening visits in the order as shown in Figures 2 and 3 as per the trial manual. However, the order may vary depending on the location of instruments at site.

[figure not shown]
- 1. Medical History⁺ and ophthalmic examination[‡]
- 2. Visual field by confrontation
- 3. Visual Acuity (distance and near), reading speed, refraction, contrast sensitivity
- 4. Testing with external telescope
- 5. Fundus photography
- 6. Ocular Coherence Tomography (OCT)
- 7. Fundus Fluorescein Angiography (FFA)
- 8. Specular microscopy
- 9. Microperimetry with assessment of PRL (sites with equipment available only)
- 10. Orthoptic assessment[#] and assessment of ocular dominance

[†]: Medical history will include general medical history, ophthalmic medical history, blood pressure measurement and recording of concomitant medication. [‡]: Ophthalmic examination will include slit lamp assessment, pupillary assessment, intraocular pressure measurement and fundoscopy. [#]: Orthoptic assessment will include history of binocular vision anomalies, cover test, record of ocular

movements, prism cover test, Bagolini glasses assessment, near point of convergence (NPC) assessment, measurement of horizontal fusional reserves and assessment of ocular dominance.

Eligibility may be determined at any of points 1-8 above based on the inclusion/exclusion criteria as specified in the protocol. Points 9-10 will provide information for the mechanistic evaluation but will not form part of the eligibility criteria. Data will be recorded on paper CRFs and the PI will confirm eligibility using an eligibility checklist. The PI will notify the NICTU of a new eligible participant.

A screening log will be maintained by the PI or designee at each site which will include data on the numbers of potential participants meeting initial eligibility for the trial but not entered into the trial. A fully anonymised minimal dataset will be recorded on these potential participants (screening number, age, gender, type of AMD (GA or wet) and reason for non-enrolment).

[figure not shown]
[figure not shown]

Figure 4. Flowchart of Screening Procedures: Screening visit 2

